7.2 Analysis of Secondary Immunogenicity Endpoints (Traditional Approach)

The analysis of secondary immunogenicity endpoints will be descriptive with no formal statistical testing. The PP analysis set will be the primary population for analysis as the results of this population are of primary interest when selecting dose/formulation for further study. The FAS may be used to provide a supportive analysis if a large number of participants are excluded from the PP analysis. No missing data will be imputed.

Titers/concentrations reported below the lower limit of quantification (LLOQ) will be set to half that limit (ie, if LLOQ=10, then 10/2 = 5) for use in computations.

7.2.1 HAI and MN Titors for Influenza Strains

As a secondary objective, serum HAI antibody response (assayed with wild-type VLP reagents) at Day 28 (post-first dose of trial vaccine), Day 56, and Day 70 (post-second dose of trial vaccine) and at other follow-up time points (Days 84 and 182), against 4 vaccine-homologous strains, and at least 1 antigenically drifted A or B strain will be assessed. In addition, neutralizing antibody responses (assayed with wild-type virus) against 4 vaccine-homologous strains, and at least 1 antigenically drifted A or B strain will be conducted. For both homologous and heterologous (ie, antigenically drifted) influenza strains, and for both results arising from HAI assay and MN assay, titer data will be summarized by GMT, GMFR, SCRs and SPRs.

The derived/calculated endpoints of HAI antibody response will include:

- Geometric mean titer (GMT) – defined as the antilog of the mean of the log-transformed HAI titers on Days 0, 28, 56, 70, 84 and 182.
 - HAI GMTRs will be summarized by the study vaccine group and visit day along with the corresponding 2-sided 95% CIs, by exponentiating the corresponding log-transformed means and their 95% CIs.
- GMFR_{Post/Pre} – defined as the within group ratio of post-vaccination to pre-vaccination (Day 0) HAI GMTRs, on Days 28, 56, 70, 84 and 182.
 - HAI GMFR_{Post/Pre} for each study vaccine group will be conducted using paired t distribution. A sample SAS code is given below:

```
proc ttest data= HAIdata alpha=0.05;
  by Treatment Visit;
  PAIRED log(HAI_D28)*log(HAI_D0);
run;
```

- HAI GMTR between selected study vaccine groups at post-vaccination time points (adjusted for intergroup variation in baseline [pre-vaccination] titers) and two-sided 95% CI will be calculated on log-transformed titers using the analysis of covariance (ANCOVA) with the study vaccine group and baseline (Day 0) measurement as the covariates under two-sided type I error rate of 0.05. No type I error rate will be adjusted.
 - Groups A-N (experimental vaccine) individually after 1 dose at Day 28 to Group O (reference vaccine) after 1 dose at Day 28
 - Groups A-N (experimental vaccine) individually after 2 doses at Day 70 to Group O (reference vaccine) after 1 dose at Day 28
 - Sample SAS code for GMTR between study vaccine groups is given below:

```
proc mixed data= HAIdata;
  class Treatment;
  model log(HAI) = log(HAI_D0) Treatment;
  lsmeans Treatment/cl diff e alpha=0.05;
```

run;

- SCR – defined as proportion of participants with either a baseline reciprocal (Day 0) titer of < 10 and a post-vaccination reciprocal titer ≥ 40 , or a baseline reciprocal (Day 0) titer of ≥ 10 and a post-vaccination titer ≥ 4 -fold higher than the baseline titer as measured on Days 28, 56, 70, 84 and 182.
- SCR and corresponding 2-sided exact binomial 95% CIs will be calculated using the Clopper-Pearson method with the following sample SAS code:

```
proc freq data=HAIdata nopolish;  
  by Treatment Visit;  
  tables seroconvind / binomial(exact) alpha=.05;  
  output out=out1 binomial;  
  
run;
```

- Two-sided 95% CIs of the difference in SCRs in HAI titers for the above cited comparisons of HAI GMTR will be based on the Miettinen and Nurminen method with the following sample SAS code:

```
proc freq data=HAIdata;  
  by Visit;  
  tables trtarm*scr / missing riskdiff (cl=MN);  
run;
```

- SPR – defined as the proportion of participants with a reciprocal HAI titer ≥ 40 on Days 28, 56, 70, 84 and 182.
 - SPR and corresponding 2-sided exact binomial 95% CIs will be constructed similarly using the Clopper-Pearson method.

The derived/calculated endpoints of MN_{50} antibody responses specific for the influenza HA will include the same assessments of GMT, $GMFR_{Post/Pre}$, GMTR, SCR, SCR differences, and SPR as for HAI antibody response.

Graphical presentations of the data (e.g., reverse cumulative distribution curves, boxplots, correlation plots) may be generated.

Participants indicating a lab-confirmed episode of influenza prior to the visit being analyzed may be excluded from the calculations. If this is implemented, it will be determined via a review of unsolicited adverse event data.

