Interventions	
Each participant will receive 2 injections, the first dose on Day 0 and the second dose on Day 56 in the same deltoid (except for participants in Vaccine Group O who will receive a third injection at Day 70). Treatments will comprise 1 of 16 regimens of investigational vaccines delivering either:
 

• One of 14 formulations of an ICC vaccine (comprising 12 unique formulations and 2 pairs of duplicate formulations) containing 1 of 4 dose levels of influenza HA protein (5, 10, 35, or 60 µg) and 1 of 3 dose levels of SARS-CoV-2 rS protein (2.5, 7.5, or 22.5 µg) with Matrix-M1 adjuvant (50 µg); in a two-dose regimen (Vaccine Groups A-N); OR

• A reference formulation of SARS-CoV-2 rS (5 µg) nanoparticle vaccine with Matrix-M1 adjuvant (50 µg), in a two-dose regimen (Vaccine Group P); OR

• A reference formulation of qNIV (60 µg HA per strain) vaccine with Matrix-M1 adjuvant (75 µg), followed by a reference formulation of SARS-CoV-2 rS (5 µg) nanoparticle vaccine with Matrix-M1 adjuvant, in a two-dose regimen, (Vaccine Group O).

 
The antigens and adjuvant dose values in the Study Design Table are nominal and reflect target doses. The qNIV antigen, SARS-CoV-2 rS antigen, and Matrix-M1 adjuvant will each be available in separate drug product vials and will be mixed in the clinic prior to administration to achieve the target doses of ICC, qNIV with Matrix-M1 adjuvant, or SARS-CoV-2 rS with Matrix-M1 adjuvant (actual doses will be within <math>\pm</math> 10% to 20% of intended target doses). Details of the final product mixing schemes to be implemented by the site pharmacist or designee, the actual content of doses achieved by the in-clinic mixing of drug product lots, and injected volumes used are provided in the Pharmacy Manual.
 
For all doses of test article, the assigned vaccine will be administered by IM injection in an approximate total volume of 0.3 to 1.0 mL.

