7 ANALYSES ADDRESSING PROTOCOL OBJECTIVES

7.1 Analyses of Primary Endpoint of Safety

The analysis of the primary safety endpoints will be descriptive and based on the Safety Analysis Set. Safety will be summarized by individual study vaccine group (groups A and C will be combined as will be groups H and N) including solicited AEs over 7 days after each of the first and second doses, unsolicited AEs over 70 days after the first dose by MedDRA preferred term, and MAAEs, SAEs, and AESIs over 6 months (approximately 182 days) after first dose. All AEs, including MAAEs, SAEs, and AESIs will be tabulated by severity, and relatedness. Missing data will not be imputed.

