7.2.2 ELISA (IgG) Concentration and MN_{50} Titers for SARS-CoV-2

Serum (IgG) antibody responses (ELISA) for vaccine homologous SARS-CoV-2 rS antigen and cross-reactive virus variants, if available, will be conducted. For the serum IgG antibody levels specific for the rS antigen(s) as detected by ELISA, the derived/calculated endpoints of IgG antibody response will include: GMEU, GMEUR, $GMFR_{Post/Pre}$, SCR, which will be calculated in manner similar to HAI antibodies described above. Further description of the analyses for GMEUR appear at the end of this section.

MN_{50} antibody responses for vaccine homologous SARS-CoV-2 rS antigen and cross-reactive virus variants, if available, will be conducted. The derived/calculated endpoints of MN_{50}

antibody responses specific for SARS-CoV-2 wild-type will include the same assessments of GMT, GMFR_{Post/Pre}, GMTR, SCR as HAI antibody response.

The definition of seroconversion is a post-vaccination concentration/titer \geq 4-fold higher than baseline. Participants indicating evidence of infection with SARS-CoV-2 prior to the time point analyzed may be excluded from the calculations. This will be determined by examining the anti-NP results taken at Day 70 and/or Day 182. An alternative measure, seroresponse, may be explored which is defined as participants having a value or fold-rise greater than the 95th percentile of values in a reference group, which would be chosen if this analysis is performed and described in the study report.

Between-group GMEUR of IgG and MN antibodies to SARS-CoV-2 will be calculated at post-vaccination time points (adjusted for intergroup variation in baseline [pre-vaccination] values) and two-sided 95% CI will be calculated on log-transformed values using the analysis of covariance (ANCOVA) with the study vaccine group and baseline (Day 0) measurement as the covariates under two-sided type I error rate of 0.05. No type I error rate will be adjusted.

- Groups A-N (experimental vaccine) individually after 1 dose at Day 28 to Group P (reference vaccine) after 1 dose at Day 28
- Groups A-N (experimental vaccine) individually after 2 doses at Day 70 to Group P (reference vaccine) after 2 doses at Day 70

Two-sided 95% CIs of the difference in SCRs for IgG and MN antibodies to SARS-CoV-2 for the above cited comparisons of GMEUR will be based on the Miettinen and Nurminen method with the following sample SAS code:

```
proc freq data=SARSdata;
  by Visit;

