7.3 Analysis of Exploratory Immunogenicity Endpoints

CMI responses to the various formulations/regimens in terms of peripheral blood CD4+ T cells which express one or more cytokines or activation markers (e.g. CD40L, INF-gamma, IL-2, TNF-alpha, IL-13) in response to in-vitro stimulation with strain-specific HA or rS will be assessed. Analysis of exploratory CMI response endpoints will be performed on a subset of approximately 50% of all participants chosen based on site location and feasibility of testing at Days 0, 7, 63 and 182 measured by ICCS and/or ELISpot assay. CMI results may be reported as an addendum to the main CSR.

The analysis for CMI response may include:

- Counts and/or proportions at Day 0, 7, 63, and 182 will be summarized by study vaccine, strain, and visit.

- Geometric mean counts (GMC) calculated as the antilog of the mean of the log-transformed counts at Day 0, 7, 63, and 182 will be summarized by study vaccine, strain, and visit.
- Geometric mean fold rise (GMFR) of counts between post-vaccination (Day 7/63/182) and pre-vaccination (Day 0) will be summarized by study vaccine, strain, and visit.
- GMCR – between-group ratio of geometric mean of counts for interested comparisons at Day 7, 63, and 182, adjusted for intergroup variation in baseline [pre-vaccination] counts.
 - The log10 values will be used to construct a 95% CI using the analysis of covariance (ANCOVA) with the study vaccine group and baseline at Day 0 as the covariates

Graphical presentations of the analyses (e.g., boxplots, bar graphs with corresponding 95% CIs, reverse cumulative distribution curves) may be generated.

Further details for data handling of CMI data will be provided by Novavax laboratory scientists at the time of analysis. Examples include LLOQ values for individual cytokines, whether background values need to be subtracted, handling zero or negative counts, and units for reporting.

Immune response to the various formulations/regimens in terms of human angiotensin-converting enzyme 2 (hACE2) inhibition antibodies will be analyzed descriptively in a manner similar to the summaries described for IgG antibody concentration and MN₅₀ antibody titers for SARS-CoV-2 (reference Section 7.2.2).

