Factor (unit)	Role	Lower value	Upper value
SARS-CoV-2 rS (μg)	Continuous	2.5	22.5
HA per strain (μg)	Continuous	5	60

Table 6 shows the planned list of runs identified by the DOE platform within SAS JMP and number of planned replicates per run. The actual number of replicates providing data will be dependent on the enrollment into the study and exclusion of subjects from the PP Analysis Set. Runs 1 and 3, as well as 8 and 14, are identically specified.

Table 6 Planned List of Runs

Run	Replicates	Value for SARS-CoV-2 Factor	Value for HA Factor
1	40	22.5	60
2	40	2.5	10
3	40	22.5	60
4	40	7.5	10
5	40	22.5	10
6	40	7.5	35
7	40	22.5	5
8	40	2.5	60
9	40	7.5	5
10	40	2.5	5
11	40	22.5	35
12	40	2.5	35
13	40	7.5	60
14	40	2.5	60

Factor levels are treated as continuous coded values ranging from -1 to 1 so that each factor contributes equally to predicting the optimal response. The initial full regression model to be run is expressed as:

$$Y = \beta_0 + \beta_1 X_1 + \beta_2 X_2 + \beta_3 X_1 X_2 + \beta_4 X_1^2 + \beta_5 X_2^2 + \varepsilon$$

where:

Y is the response

X1 = coded antigen level for each HA flu strain

X2 = coded antigen level for SARS-CoV-2 rS

X1*X2 = interaction term for HA antigen level and SARS-CoV-2 rS antigen level

ϵ = error term with expected value of 0

SAS JMP will be used to fit a least-squares model for each response indicated in Table XX. Each run's replicate values may or may not be averaged across the subjects in the PP Analysis Set to determine the independent Y value for the run. An examination of the data will guide the decision and it will be documented in the report. Baseline measurement for each replicate may be included as covariate if no averaging is performed for a run's replicates. The initial full model will be run and significance of each term examined. A p-value <0.05 indicates that a term is significant. Non-significant terms will be removed and the resulting reduced model (for each response) will be fitted for exploration with a Predication Profiler tool. Desirability functions (ranging from 0 for lowest level to 1 for highest level) will be used to identify factor settings that optimize the set of responses. Weighting for each response may be considered. Factor setting(s) that lead to the highest overall desirability will be the level of HA and rS that optimize responses in Table XX.

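### Identical formulations A/C and H/N are pooled for safety but not for immunogenicity, and the ANCOVAs omit the age stratum used in randomisation (minor)

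*SAP*

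**What the plan says.** **Duplicate formulations.** The protocol synopsis describes the 14 ICC groups as "comprising 12 unique formulations and 2 pairs of duplicate formulations". In the dosing tables (Protocol Table 3, SAP Table 1), A and C share one pair of antigen doses and H and N share another. SAP 7.4 confirms it: "Runs 1 and 3, as well as 8 and 14, are identically specified".

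**Safety.** SAP 7.1 states that "groups A and C will be combined as will be groups H and N". The risk differences listed in SAP 7.1.1 nevertheless take Groups A to N one at a time.

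**Immunogenicity.** No pooling rule appears.
- SAP 7.2.1, HAI and influenza MN ratios: "Groups A-N (experimental vaccine) individually after 1 dose at Day 28 to Group O (reference vaccine) after 1 dose at Day 28".
- SAP 7.2.2, SARS-CoV-2 IgG and MN ratios: "Groups A-N (experimental vaccine) individually after 2 doses at Day 70 to Group P (reference vaccine) after 2 doses at Day 70".
- Seroconversion differences follow the same list: "Two-sided 95% CIs of the difference in SCRs in HAI titers for the above cited comparisons of HAI GMTR".
- Within-group fold rise "for each study vaccine group will be conducted using paired t distribution"; the GMT, SCR and SPR summaries are also by group.
- SAP 7.3 says CMI results "will be summarized by study vaccine, strain, and visit", which does not settle whether a duplicated pair counts as one study vaccine or two.

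**Age.** Randomisation is stratified at 60 years (SAP 1.1 and 1.3, Protocol 7.2.2). Every ANCOVA (SAP 7.2.1 with its sample code, SAP 7.2.2, SAP 7.3, Protocol 9.3.2) contains only vaccine group and the baseline value. SAP 11.2 names only the pre-vaccination titer.

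**The concern.** The SAP accepts for safety that two groups receiving the same formulation estimate one quantity, then sets that aside for immunogenicity. SAP 7.2 says the per-protocol immunogenicity results are what matters most when a formulation is chosen for further study, so these tables will be read beside the response surface. For two formulations the reader would see two geometric means, two ratios to the reference and two seroconversion rates, each less precise than the data allow. Any difference within a pair would be noise that could be mistaken for signal.

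In safety, 7.1 and 7.1.1 can be read in different ways, so two programmers could build different risk-difference tables.

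The age point is smaller. A factor used to stratify randomisation is normally carried into the model, and the plan gives no reason for leaving it out.

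**Working it through.** **Inputs.** From the documents: 40 participants per group (Protocol 9.2.1, SAP 1.2), so 80 for A+C or H+N; two-sided 95% intervals; a CMI subset of about 50% (SAP 3.4.2), so about 20 per group if it is evenly spread. Assumed, because the documents do not give them: log10 SD of 0.3 to 0.6, seroconversion rates of 30% to 90%, and equal age strata.

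**The plan's own figures.** None bears directly on this point. Those with full inputs reproduce: 1 − 0.95^40 = 87.1% (stated 87%), and 1 − (1 − 0.00534)^560 = 95.0% (stated 95%). The stated power above 99% for a two-fold difference has no SD. Read as a two-group comparison, it needs log10 SD ≤ 0.301 / [(1.960 + 2.326) × √(2/40)] = 0.314, close to the lower end of the range assumed here.

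**Ratios against the reference (GMTR, GMEUR).**
- SE ratio, pooled to split: √(1/80 + 1/40) / √(2/40) = 0.866.
- 1/0.866 − 1 = 15.5% wider when split, whatever the SD. Going from 20 vs 20 to 40 vs 20 for the CMI ratio (GMCR) gives the same 0.866.
- 95% CI factor, 10^(1.96 × SD × √(1/n₁ + 1/n₂)): 1.35 to 1.83 split, 1.30 to 1.69 pooled.

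**Group geometric means and fold rises.**
- Half-width in SD units: t(0.975, 39)/√40 = 0.3198 against t(0.975, 79)/√80 = 0.2225; ratio 1.437, so 43.7% wider.
- GMT factor: 1.25 to 1.56 at n = 40, 1.17 to 1.36 at n = 80.
- CMI, 20 against 40: 0.4680/0.3198 = 1.463, so 46.3% wider.

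**Group SCR and SPR (Clopper-Pearson width, percentage points).**

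| Observed rate | n = 40 | n = 80 |
|---|---|---|
| 30% or 70% | 30.0 | 21.0 |
| 50% | 32.4 | 22.8 |
| 90% | 20.9 | 14.3 |

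Split intervals are 42% to 46% wider.

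**SCR differences (Miettinen-Nurminen width, percentage points; excess from unrounded widths).**

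| ICC vs reference | 40 vs 40 | 80 vs 40 | Wider when split |
|---|---|---|---|
| 50% vs 50% | 43.1 | 37.2 | 15.6% |
| 70% vs 70% | 40.1 | 34.6 | 16.1% |
| 90% vs 90% | 29.5 | 24.8 | 18.9% |
| 90% vs 50% | 36.1 | 32.8 | 9.8% |
| 50% vs 90% | 36.1 | 29.5 | 22.4% |

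The last two rows are the extremes over all combinations of 30, 50, 70 and 90%.

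**Chance gap within a pair.** The reference cancels, so the median ratio of the two GMTRs is 10^(0.6745 × SD × √(2/40)) = 1.11 to 1.23.

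**Age.** With equal strata, leaving age out inflates the interval by √(1 + (log10(fold)/2)² / SD²) − 1:

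| Age effect | SD 0.3 | SD 0.6 |
|---|---|---|
| 1.1-fold | 0.24% | 0.06% |
| 1.2-fold | 0.87% | 0.22% |
| 1.3-fold | 1.79% | 0.45% |
| 1.4-fold | 2.92% | 0.74% |
| 2-fold | 11.9% | 3.1% |

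The 1.3- and 1.4-fold values are in Protocol 2.1.5.2.3 (18–64 against 65–84 years). The 2-fold value is in Protocol 2.1.5.2.1 (18–59 against 60–84 years).

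**The case against.** Separate reporting can be defended. Participants are randomised to 16 groups, Protocol 9.3.2 asks for summaries by treatment group, and taking A to N one at a time is a clear instruction that a programmer can follow. Showing the replicates apart also displays how well they agree. No formal test or decision rule rests on these tables. The response-surface model enters antigen levels rather than group labels, so it already uses the pairs as replicates. SAP 7.1.1 sits under 7.1 and can be read as inheriting its pooling. In SAP 7.3, study vaccine may already mean formulation, and the even CMI split is uncertain because that subset is chosen by site. On age, stratification already balances the groups, and the gain may be negligible.

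Most of this stands, and it is why the point is minor. It does not explain why one SAP treats a pair as one formulation for safety and as two for immunogenicity. The replicate check survives if the separate groups stay as supportive output. A reading that has to be inferred in 7.1.1 and 7.3 is better written down. On age, the 2-fold effect has its cut at this trial's stratum boundary, so the gain could exceed 3%. Its age bands are much wider than 50 to 70 years, however, it concerns SARS-CoV-2 neutralising antibody only, and the baseline titer may absorb part of it.

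**Conclusion.** The point holds at minor weight. For two of the 12 formulations the plan gives up precision already in the data: 15.5% of log-scale interval width for ratios against the reference, 43.7% for group GMTs and fold rises, 42% to 46% for group SCR and SPR, and 9.8% to 22.4% for SCR differences. The first two follow from the planned group sizes whatever the SD. The last two rest on assumed rates of 30% to 90%, and the absolute CI factors on an assumed log10 SD of 0.3 to 0.6. Actual per-protocol numbers will shift all of them somewhat.

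Leaving out age costs 0.1% to 0.9% for a 1.1- to 1.2-fold effect, which seems the likelier range between two adjacent decades, and 0.4% to 2.9% for 1.3- to 1.4-fold. The documents do not give the effect at this trial's own age split. Neither omission biases an estimate.

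**What to change.** - **SAP 7.2.1, 7.2.2, 7.3:** state that A+C and H+N are combined for the group summaries (GMT/GMEU, GMFR, SCR, SPR, CMI) and for the GMTR, GMEUR, GMCR and SCR-difference comparisons. Show the four groups separately as supportive output.
- **SAP 7.1.1:** reword the risk differences to refer to each unique formulation, with A+C and H+N combined, so that they agree with 7.1.
- **SAP 7.2.1, 7.2.2, 7.3, 11.2:** add the two-level age stratum as a fixed effect in the ANCOVAs.
- **SAP 12:** record these as changes from Protocol 9.3.2, which specifies summaries by treatment group and an ANCOVA without age.
- **SAP 7.4:** no change.

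The cost is a few sentences, one derived formulation variable and one model term. No new data are needed and no information is lost.

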7.4 Analysis of Immunogenicity Endpoint Using the DoE Approach

The study's 12 unique vaccine formulations (excluding reference formulations) arose from a DoE approach with the objective to construct one or more response surface models that can provide information on combination(s) of antigen quantities (both HA and rS) that when combined with 50 µg of Matrix-M1 adjuvant will maximize HAI and anti-S immune responses. The combination(s) identified may or may not be the formulations that are currently being studied. The goal of response surface modelling is to establish the relationship between response and one or more factors, using a set of tools to identify factor settings which optimize response. The results are intended to inform selection of potential dose levels for further study. The modelling exercise will consist of a prospectively established set of analyses and may be followed by further exploration. The SAP defines the prospective set of analyses, whereas further exploratory modelling will be described in the clinical study report.

Day 28 (post single dose) and Day 70 (post 2 doses) immune responses will be the data of primary interest for the regression analysis. Participants in the study are baseline seropositive for SARS-CoV-2 and can be expected to have previously exposure to influenza viruses, so baseline antibody levels for the response parameters are likely to vary and be predictive of response at Days 28/70. Therefore, participants with non-missing Day 28/70 and baseline values in the PP Analysis Set for the responses of interest (Section 7.3.1) will be included in the modeling. In response surface modelling, treatment group is not explicitly designated as an independent variable but are indirectly reflected by factor levels that account for the

amount of each antigen (HA or rS) received. These are treated mathematically as coded continuous quantities ranging from -1 to 1. Participants having a lab-confirmed case of influenza (determined via examination of adverse event reporting) or COVID-19 (determined by anti-NP) between Day 0 and Day 70 may be excluded for the modeling to reduce the extra variability arising from such data points.

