11.2 Adjustments for Covariates

Comparison of GMTR/GMEUR between the study vaccine groups will be adjusted for pre-vaccination titer.

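### Seroconversion-rate differences are not adjusted for Day 0 titre at the comparison step, although the GMT and GMEU ratios for the same pairs are; adjusting them could narrow some descriptive intervals

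*SAP*

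**What the plan says.** SAP 7.2.1 compares each of Groups A to N with Group O on the influenza assays. SAP 7.2.2 compares each of them with Group P on the SARS-CoV-2 assays. Every comparison is made on two scales.

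- **Ratio (GMTR or GMEUR).** Log values are analysed by "analysis of covariance (ANCOVA) with the study vaccine group and baseline (Day 0) measurement as the covariates".
- **SCR difference.** For influenza, "Two-sided 95% CIs of the difference in SCRs in HAI titers for the above cited comparisons of HAI GMTR will be based on" the Miettinen-Nurminen method. The sample code, "tables trtarm*scr / missing riskdiff (cl=MN", crosses arm with seroconversion status and carries no covariate or stratum. SAP 7.2.2 repeats this: "Two-sided 95% CIs of the difference in SCRs for IgG and MN antibodies to SARS-CoV-2 for the above cited comparisons of GMEUR" use the same method and the same code.

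SAP 11.2 confines adjustment to the first scale: "Comparison of GMTR/GMEUR between the study vaccine groups will be adjusted for pre-vaccination titer". It does not mention SCR and gives no reason for the difference.

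Two other statements matter. Seroconversion is itself relative to Day 0. For HAI it is a titre at least 4-fold "higher than the baseline titer as measured on Days 28, 56, 70, 84 and 182", with a separate rule (reaching 40) for those starting below 10. For SARS-CoV-2 it is a plain 4-fold rise. SAP 7.4 says, about the modelled antibody responses, that "baseline antibody levels for the response parameters are likely to vary and be predictive of response at Days 28/70". SAP 7.2 describes all these secondary analyses as descriptive, without formal testing.

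**The concern.** If Day 0 titre predicts who seroconverts, a crude difference in proportions leaves explainable variation in the standard error, and the interval is wider than it need be. A chance imbalance in Day 0 titre also shifts the crude SCR difference, while the ANCOVA ratio for the same pair is corrected for it. The reference group's Day 0 values enter all 14 contrasts against it, so one unusual draw moves the whole SCR column the same way.

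The stake is precision in a descriptive table. SAP 7.2 does say that the per-protocol immunogenicity results are of main interest for choosing a formulation, so the SCR columns will be read. But selection is to come from the DoE response-surface models.

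**Working it through.** **1. The plan's own figure.** No precision figure is given for SCR differences. The only one for immunogenicity is more than 99% power for a two-fold difference with 40 per group (SAP 1.2). It cannot be reproduced because no SD is stated; as a two-group comparison it needs an SD of at most 0.314 log10. It does not bear on SCR.

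**2. The crude interval.** SE = √[2p(1−p)/40]. At p = 0.50 this is √(0.50/40) = 0.112; at p = 0.75 it is √(0.375/40) = 0.097. The simulated Miettinen-Nurminen half-widths were about 21 and 19 percentage points.

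**3. When Day 0 predicts seroconversion.** On the log2 scale let post = a + b × baseline + error. The rise is then a − (1−b) × baseline + error. At b = 1 the rise does not depend on baseline, and under the plain 4-fold rule adjustment gains nothing. At b < 1 a high baseline makes a 4-fold rise harder.

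**4. SARS-CoV-2 rule.** Assumed: baseline SD 1.8, error SD 1.3 (log2), SCR 60%, 40 v 40, no true difference.

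- Correlation of rise with baseline: ρ = −(1−b)·1.8 / √[((1−b)·1.8)² + 1.3²].
- Correlation of seroconversion with baseline: r = ρ × 0.386/√(0.6 × 0.4) = 0.79ρ, where 0.386 is the normal density at the 60% point.
- Approximate SE ratio, adjusted to crude: √(1 − r²).

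At b = 0.6: ρ = −0.72/√(0.518 + 1.69) = −0.485; r = −0.38; ratio √(1 − 0.146) = 0.92. Simulation (2,000 trials per scenario; risk difference standardised from a logistic model on arm and log Day 0 titre) agrees:

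| Slope b | r | √(1−r²) | Simulated SE ratio | Equivalent extra participants (1/ratio² − 1) |
|---|---|---|---|---|
| 1.0 | 0 | 1.00 | 1.005 | −1% |
| 0.8 | −0.21 | 0.98 | 0.986 | 3% |
| 0.6 | −0.38 | 0.92 | 0.925 | 17% |
| 0.4 | −0.50 | 0.86 | 0.859 | 35% |
| 0.2 | −0.59 | 0.81 | 0.800 | 56% |

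**5. HAI rule.** With the SAP's example LLOQ of 10, a value below it is set to 5, so reaching 40 is an 8-fold rise (40/5). That makes seroconversion harder at low baseline and partly offsets the gradient in step 3. Same SDs, assumed baseline GMT 40:

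| Slope b | r (SCR 50% / 75%) | SE ratio (SCR 50% / 75%) |
|---|---|---|
| 1.0 | +0.12 / +0.16 | 1.002 / 0.996 |
| 0.8 | −0.07 / −0.05 | 1.004 / 1.005 |
| 0.6 | −0.25 / −0.25 | 0.970 / 0.968 |
| 0.4 | −0.41 / −0.42 | 0.924 / 0.893 |
| 0.2 | −0.53 / −0.54 | 0.829 / 0.823 |

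At slope 0.4 and SCR 75% the half-width falls from 19.0 to 16.9 points. A further simulation with the HAI rule and an indicator for Day 0 below 10 gave ratios from about 0.99 to 0.83.

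**6. What the indicator adds.** With baseline SD 1.5, slope 0.5 and error SD 1, the variance reduction under the HAI rule was about 0%, 3% and 13% at baseline GMT 10, 20 and 40. With the indicator it was about 5%, 8% and 14%, that is SE ratios of √0.95 = 0.97, √0.92 = 0.96 and √0.86 = 0.93.

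**7. Chance imbalance.** One standard error of the Day 0 mean difference is SD × √(2/40): 0.34 log2 at SD 1.5 and 0.40 at SD 1.8. Under the plain 4-fold rule this moves the crude SCR difference by about 5 to 6 points at slope 0.5 and about 3 at slope 0.7. At slope 0.5 the adjusted estimate moves by less than half a point.

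**8. Coverage.** The adjusted 95% interval covered in about 93% to 95% of trials.

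**The case against.** The best defence is that baseline is already in the endpoint. Every seroconversion value is a rise over the participant's own Day 0 titre, and SAP 7.4 itself offers the individual fold rise as a way to bring in baseline variation. The SAP's sentence on prediction concerns antibody response, not seroconversion, and Day 0 can predict the post-vaccination titre strongly yet say nothing about a 4-fold rise. Each pair also has a baseline-adjusted contrast in the GMTR or GMEUR. The crude SCR difference equals the difference of the tabulated rates beside it, and Miettinen-Nurminen behaves well at 40 v 40.

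Most of this stands, and it limits the point. It does not remove it: under the plain 4-fold rule, dividing by baseline takes out its influence only when the slope is 1, and the SAP does not assume that. Its ANCOVA estimates the slope, and its parallel PROC RSREG model enters the Day 0 value as a covariate. For HAI and influenza MN, the rule change at 10 ties seroconversion to Day 0 even at slope 1, though in step 5 that alone gave no useful gain.

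A reader might infer that the SCR differences ignore Day 0 titre altogether. They do not; only the comparison step leaves it out. A reader might also blame baseline alone if a GMTR and an SCR difference disagree. A mean ratio and a threshold proportion can disagree for other reasons, and adjustment would not guarantee agreement.

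**Conclusion.** The two scales are treated differently without a stated reason, and adjusting the SCR comparison can help. Over the assumed range (slope 0.2 to 1.0, log2 baseline SD 1.8, error SD 1.3, SCR 50% to 75%, 40 v 40) the SE of the SCR difference falls by 0% to about 20%. The gain is nil or negligible at slopes of about 0.8 and above, and moderate to large only at low slopes. The documents give no baseline SD, slope or SCR, so where this trial lies is unknown, and per-protocol exclusions will reduce the 40 per group.

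The documents do not support saying that the planned intervals are certainly less precise than the data allow, that they are biased, or that power is lost. The crude interval is valid over randomisation and the contrasts are descriptive. The DoE models use fold rise, or absolute values with or without baseline as a predictor, and are unaffected. This is an inexpensive improvement, not a defect that threatens a conclusion.

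**What to change.** In SAP 7.2.1, 7.2.2 and 11.2, pre-specify for each listed SCR comparison a Day 0-adjusted marginal risk difference:

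- logistic regression of seroconversion on vaccine group and log10 Day 0 value, plus an indicator for Day 0 below 10 for HAI and influenza MN;
- predictions standardised over the pooled Day 0 values of the two groups;
- a robust 95% CI.

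Report it beside the planned Miettinen-Nurminen interval, which is retained and is the only interval shown when SCR is 0% or 100% in either group. The estimand stays the marginal difference in SCR.

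The cost is a few sentences, a short program and one more table column, with no new data. The downsides are the slightly low coverage of the adjusted interval and the need to state the 0%/100% rule in advance.
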